### 4.1.4 Exploratory Endpoints

Any comparisons between groups (Cingal, Placebo, TH), within groups and / or time points (from baseline through to 26 weeks) not described in the primary or secondary endpoints may be presented in the exploratory endpoints including:

- EuroQoL (EQ-5D)
- WOMAC Pain Score (100mm VAS)
- OMERACT-OARSI
- Total WOMAC
- WOMAC Stiffness Score
- WOMAC Physical Function Score
- Patient Global Assessment
- Evaluator Global Assessment
- Range of Motion
- Rescue Medication Usage: Difference in analgesic use measured by number of pills taken between visits will be compared between treatment groups descriptively.
- Number of Subjects Considered Treatment Failures: Treatment Failure: A subject who undergoes a procedure or uses a medication (other than the rescue medication) for the

treatment of OA in the index knee at any time after the study injection through the 12 week visit.

For the exploratory analyses, the continuous variables will be analyzed via an analysis of variance and contrasts used to assess the prescribed comparisons. For the discrete variables, a Fisher's exact test will be used to assess the desired comparisons.

#### 4.2 STATISTICAL METHODS

Tabulation of summary statistics, graphical presentations, and statistical analyses will be performed using SAS® software 9.4 or higher version. Where not otherwise specified, the last pretreatment observation will be used as baseline for calculating post-treatment changes from baseline. The primary presentations and analyses will be based on data pooled across study centers. Relevant summaries for individual centers, or combinations of centers, may be presented for primary data. All testing and confidence intervals will use a significance level of 5%.

# 4.3 DEMOGRAPHIC AND BASELINE CHARACTERISTICS

All demographic and baseline characteristics will be tabulated by treatment group and a test of homogeneity between the treatment groups will be conducted. For continuous variables (e.g. age, height, weight) a one way ANOVA will be used. For categorical variables (e.g. gender, race), a Fisher's exact test or chi-squared test will be used. Medical history findings, physical examinations and concomitant medications will be tabulated by treatment group.

The baseline Chemistry, Hematology, Urinalysis, Vital Signs, and BMI data will be summarized via descriptive statistics and tested for homogeneity using a one way ANOVA.

#### 4.4 ADVERSE EVENTS

All AEs will be coded according to MedDRA. Safety assessments will include Treatment-Emergent Adverse Events (TEAEs) which are defined as AEs with an Investigator assessment of definitely, probably, or possibly related to CTM. TEAEs will be summarized with frequencies and percentages by system organ class and preferred term, severity, and relationship to study CTM for each treatment group. In summaries of TEAEs by severity and relationship to CTM for subjects reporting multiple episodes, all reported events will be included, not only the worst reported case. Serious Adverse Events will also be presented by relationship to the CTM.

The number of subjects with at least one AE will be tabulated for each treatment group. Differences between the treatment groups will be tested using Fisher's exact test. Then the number of AEs for each treatment group will also be tabulated.

The number of subjects and the number of AEs will be tabulated by severity, relationship, and local injection site specific events versus non local events.

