9.4 Baseline

The Baseline Visit will occur 14±3 days after the Screening Visit. The following assessments will take place during this visit:

- Concomitant Medications
- Confirm Rescue and Prohibited Medication Washout
- Count/Dispense Rescue Medication Pills
- Evaluate Subject Electronic Diary including daily pain scores
- Physical Evaluation (Both Knees) to be performed by Blinded Evaluator
- Range of Motion (Both Knees) to be performed by Blinded Evaluator
- Evaluator Global Assessment to be performed by Blinded Evaluator
- WOMAC (Both Knees)
- VAS Pain Scale (Both Knees)
- NRS Pain Scale (Both Knees)
- EuroQoL-5D-5L
- Patient Global Assessment
- Randomization if Subject meets all Screening and Baseline assessments (except IA aspiration)
- Aspirate Synovial Fluid
- Evaluation of Baseline Enrollment Criteria
- Intra-articular Injection to be performed by Treating Physician
- Assess Treatment-Emergent Adverse Events

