10.5 Reporting

10.5.1 Adverse Events

Only AEs that occur during and after treatment (treatment emergent AEs) will be recorded. At each visit during the trial, AEs that have occurred since the previous visit must be recorded. All subjects will be questioned and evaluated for AEs or complications associated with the procedure. Complications of the injection include, but are not necessarily limited to: pain, swelling and/or inflammation at the injection site. The Investigator will determine the severity and relationship of each event, as defined above.

AEs observed during the course of this study, regardless of severity or relationship to the injection will

be recorded on the appropriate eCRF. Each reported complication/AE will also include the duration, action taken to address the AE, and the resolution status (e.g. ongoing, resolved). These subjects will continue to be evaluated for safety and efficacy at all scheduled follow-up points.

The Sponsor must report the results of an evaluation of an Unanticipated Adverse Device Effect (UADE) to relevant regulatory agencies and all reviewing IRBs and Investigators within timelines required by the regulatory agencies.

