11.7 Adverse Events

All AEs will be coded according to MedDRA. Safety assessments will include Treatment-Emergent Adverse Events (TEAEs) which are defined as AEs with an Investigator assessment of definitely,

probably, or possibly related to CTM/study procedure. TEAEs will be summarized with frequencies and percentages by system organ class and preferred term, severity, and relationship to study CTM/study procedure for each treatment arm. In summaries of TEAEs by severity and relationship to CTM/study procedure for subjects reporting multiple episodes, all reported events will be included, not only the worst reported case. Serious Adverse Events will also be presented by relationship to the CTM/study procedure.

The number of subjects with at least one AE will be tabulated for each treatment arm. Differences between the treatment arms will be tested using Fisher's exact test. Then the number of AEs for each treatment arm will also be tabulated.

The number of subjects and the number of AEs will be tabulated by severity, relationship, and local injection site specific events versus non local events.

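### Treatment-emergent AEs are defined by relatedness rather than timing, so the only planned table by event term leaves out AEs judged unlikely or not related

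*SAP*

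**What the plan says.** The term 'treatment-emergent' is used with two meanings.

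**By timing.** Protocol 10.5.1 states: "Only AEs that occur during and after treatment (treatment emergent AEs) will be recorded". The same section adds that "AEs observed during the course of this study, regardless of severity or relationship to the injection will" be entered on the eCRF. Protocol 9.4 lists "Assess Treatment-Emergent Adverse Events" directly after the intra-articular injection, which fits a timing meaning, although that line gives no definition.

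**By relatedness.** SAP 4.4 refers to "Treatment-Emergent Adverse Events (TEAEs) which are defined as AEs with an Investigator assessment of definitely, probably, or possibly related to CTM". Protocol 11.7 has the same construction, "Treatment-Emergent Adverse Events (TEAEs) which are defined as AEs with an Investigator assessment of definitely", followed by the probable and possible categories. Neither definition contains a timing element.

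**What is tabulated.** SAP 4.4 says "TEAEs will be summarized with frequencies and percentages by system organ class and preferred term, severity, and relationship to study CTM", and Protocol 11.7 says "TEAEs will be summarized with frequencies and percentages by system organ class and preferred term, severity, and relationship to study CTM/study procedure". For all AEs, both sections plan the number of subjects with at least one AE (compared between arms by Fisher's exact test) and the total number of AEs. They also plan a breakdown: "The number of subjects and the number of AEs will be tabulated by severity, relationship, and local injection site specific events" versus non-local events. SAEs are presented by relationship.

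**The concern.** A table by arm and event term is where a reader sees that one specific event is more frequent in one arm. Its value is that it does not depend on case-by-case causality judgements: an imbalance between randomised arms can show up even when each individual event looked incidental. Restricting the table to events already judged related removes that check for every other event.

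The label is a second problem. A reader who meets 'TEAE' in the results would reasonably take it in the Protocol 10.5.1 sense, as everything that arose during or after treatment, when the table actually holds a subset selected by investigator judgement.

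The excluded group is also wider than events with an established other cause. The 'Unlikely Related' definition in Protocol 10.3 does say that other factors are the likely source, but it also says that the information available at the time does not suffice to determine causality.

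**Working it through.** This is a question of definitions, and the plan states no figure to reproduce. The check sets the sections side by side.

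1. **Relationship categories (Protocol 10.3):** definitely, probably, possibly, unlikely and not related, so 5.

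2. **Categories that count as TEAE:**

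| Source | Criterion | Categories included |
|---|---|---|
| Protocol 10.5.1 | Onset during or after treatment | 5 of 5 |
| Protocol 11.7 | Definitely, probably or possibly related to CTM or study procedure | 3 of 5 |
| SAP 4.4 | Definitely, probably or possibly related to CTM | 3 of 5, CTM only |

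 Excluded under the relatedness definitions: 5 − 3 = 2 categories. This counts categories, not events.

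3. **Where the two excluded categories appear:**

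| Planned output | Includes unlikely / not related? | By event term? |
|---|---|---|
| TEAE summary by system organ class and preferred term | No | Yes |
| Subjects with at least one AE, with Fisher's exact test | Yes | No |
| Number of AEs | Yes | No |
| Counts by severity, relationship, local/non-local | Yes | No |
| SAEs by relationship | Yes, if serious | Not stated |

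 Specified tables by event term that include these two categories: 0. SAP 1.0 mentions data listings in general, but a listing is not a table by arm and term.

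4. **CTM wording.** Protocol 11.7 refers to the CTM or the study procedure; SAP 4.4 refers to the CTM alone. Read literally, the SAP also drops AEs attributed only to the procedure. Yet Protocol 10.3 assesses relationship to the procedure and collects timing relative to the arthrocentesis for related events.

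5. **Internal fit.** TEAEs are to be summarised by relationship after two of the five relationship levels have been removed by definition.

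6. **How thin the table could be (illustration only).** Protocol 13.3.2 gives related-AE percentages from the two earlier Phase III trials: 2.0% and 7.6% for Cingal, and 4.1% for TH in one of them. The denominator is not stated. Assuming these are percentages of subjects and that they recur with 99 subjects per active arm:
 - Cingal: 0.020 × 99 ≈ 2 to 0.076 × 99 ≈ 7.5 subjects
 - TH: 0.041 × 99 ≈ 4 subjects

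 Protocol section 4 also reports that every SAE in the earlier Cingal trials was judged unrelated to the injection. If that happened again, no SAE would enter the event-term table. These figures describe what the table would contain. They do not give the number left out, because no all-AE rate is given.

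**The case against.** The strongest reply is that little is lost. Under Protocol 10.5.1 only AEs during and after treatment are recorded, so every AE in the all-AE tables is already treatment-emergent by timing. Those tables cover overall counts, severity, relationship and location, and they are compared between arms. All AEs are MedDRA-coded, and nothing in the plan forbids a further table by term. The trial is described as a pilot, and no efficacy result depends on this point.

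Much of that stands. No AE is lost, the all-AE severity tabulation already covers what a TEAE severity table would show, and an all-AE table by term is unspecified rather than ruled out. The line in Protocol 9.4 is only supportive, and Protocol 10.5.1 carries the argument by itself.

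It does not remove the problem. Counts by severity, relationship and location do not show which event occurred. The sections are not merely silent: they state a rule, and following that rule produces a table of related events under a label that Protocol 10.5.1 uses for something else. The agreement between Protocol 11.7 and SAP 4.4 does not help, since both conflict with Protocol 10.5.1. Safety remains a stated endpoint covering all AEs, pilot or not.

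**Conclusion.** The concern holds and should be fixed. One term has two incompatible meanings, and the version used for analysis confines the only specified event-term summary to 3 of 5 relationship categories. The other 2 appear in no specified table by event term. Under the SAP's narrower wording, AEs related only to the procedure also fall out.

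The consequence is limited to how safety results are presented and labelled. All AEs are still recorded, coded and counted by arm. The number or share of AEs missing from the event-term table cannot be derived from the documents. The conclusion rests on reading both sections as written, without assuming unlisted tables would be produced.

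**What to change.** 1. In SAP 4.4 and Protocol 11.7, define a TEAE by timing, in line with Protocol 10.5.1: any AE with onset during or after treatment, regardless of relationship.
2. Produce the system organ class and preferred-term table by arm on all TEAEs. All-AE severity counts are already planned and need only the consistent label.
3. Present related TEAEs as a separate subset labelled as such, with relationship to the CTM or study procedure worded identically in both documents.
4. As a minor clarification, state whether the person judging relatedness is blinded. Protocol 10.3 assigns this to the Investigator, while Protocol 9.2.22 says the unblinded Treating Physician is most often the PI.

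Cost: a definition change in each document and one extra table. The data are already recorded and coded. A change to Protocol 11.7 is an amendment and, under Protocol 15.4, needs FDA and IRB approval before implementation at sites. The table can be added through the SAP without waiting for that, with the protocol wording aligned at the next amendment.

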10.3 Relationship

The Relationship between an AE and the CTM and / or the study procedure will be determined by the Investigator on the basis of his or her clinical judgment and the following definitions:

Definitely Related: The AE follows a reasonable temporal sequence from administration of the CTM/study procedure; the AE follows a known or expected response pattern to the CTM/study procedure.

Probably Related: The AE follows a reasonable temporal sequence from administration of the CTM/study procedure; the AE follows a known or expected response pattern to the CTM/study procedure; and the AE could not be reasonably explained by the known characteristics of the

subject's clinical state.

Possibly Related: The AE follows a reasonable temporal sequence from administration of the CTM/study procedure; the AE follows a known or expected response pattern to the CTM/study procedure but could readily have been produced by a number of other factors.

Unlikely Related: The AE which etiology is unlikely related to the CTM/study procedure even if event may follow a known or expected response pattern to the CTM/study procedure, and likely to be produced by a number of other factors. Sufficient information is not available at the time of the AE to determine its causality.

Not Related: An AE for which sufficient information exists to indicate that the etiology is unrelated to the CTM/study procedure. One or more of the following variables apply:

- The AE does not follow a reasonable temporal sequence following administration of the CTM/study procedure;
- The AE is readily explained by the subject's clinical state or other therapies.

For events that are determined to be definitely, probably or possibly related, additional information on the relationship and timing of the event in relation to the arthrocentesis and study injection will be captured.

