## *3.4 SAFETY ENDPOINT:*

The incidence, timing, severity, and relationship to treatment of all Adverse Events (AE) will be collected and coded using Medical Dictionary for Regulatory Activities (MedDRA). Local injection site and non-local events will be recorded separately.

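### Treatment-emergent AEs are defined by onset in protocol 10.5.1 but by relatedness in protocol 11.7 and SAP 4.4 (which also drops the study procedure), so the only preferred-term table is incomplete

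*SAP*

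**What the plan says.** Three places fix what treatment emergent means in this trial.

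- **Protocol 10.5.1** uses onset: "Only AEs that occur during and after treatment (treatment emergent AEs) will be recorded". The same section has AEs recorded whatever their severity or causal grade.
- **Protocol 11.7** uses causality: TEAEs are AEs the investigator grades definitely, "probably, or possibly related to CTM/study procedure".
- **SAP 4.4** also uses causality, but for the product only: "which are defined as AEs with an Investigator assessment of definitely, probably, or possibly related to CTM".

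Both statistical sections then give the same main table. In the SAP's words, "TEAEs will be summarized with frequencies and percentages by system organ class and preferred term", with severity and relationship added. The remaining AE output in both documents is subjects with at least one AE per arm (compared by Fisher's exact test), the number of AEs per arm, subjects and events by severity, relationship and local versus non-local, and SAEs by relationship.

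The safety endpoint in SAP 3.4 is broad: "The incidence, timing, severity, and relationship to treatment of all Adverse Events (AE) will be collected and coded". Under protocol 10.3 the relationship to the CTM and/or the study procedure "will be determined by the Investigator on the basis of his or her clinical judgment". For events graded at least possibly related, "additional information on the relationship and timing of the event in relation to the arthrocentesis and study injection will be captured".

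**The concern.** One term carries two meanings. A reader of the clinical study report will normally take a TEAE table to list every event that began on or after treatment, and protocol 10.5.1 says the same. The table actually planned holds only events that an investigator attributed to the product, or under protocol 11.7 to the product or procedure. It would be mislabelled, and it would be incomplete as a description of what happened to subjects after injection.

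The narrowing in the SAP adds a second problem. Every subject has an aspiration attempt and an injection, and protocol 10.5.1 itself names pain, swelling and inflammation at the injection site as complications. A site could reasonably put such events down to the needle and not to the product. Protocol 11.7 keeps them in the TEAE table and SAP 4.4, read literally, does not.

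What is at stake is the descriptive safety profile. Counts by arm would be available, but for the omitted events no summary would say which events they were.

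**Working it through.** No arithmetic applies. The plan states no figure on this point, so the check is a comparison of texts.

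**Step 1: where the relatedness rule comes from.** Protocol 11.7 contains it, and SAP 4.4 follows 11.7 almost word for word. The conflict between onset and causality therefore lies inside the protocol (10.5.1 against 11.7), and the SAP inherits it.

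**Step 2: what the SAP changes.** Protocol 11.7 names the study procedure beside the CTM in four places: the TEAE definition, the main TEAE summary, the rule for multiple episodes and the SAE presentation. SAP 4.4 says CTM alone in all four and gives no reason.

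**Step 3: follow each kind of post-injection event through the definitions.**

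| Event as graded | TEAE under 10.5.1 | TEAE under 11.7 | TEAE under SAP 4.4 | In all-AE counts |
|---|---|---|---|---|
| Related to CTM | yes | yes | yes | yes |
| Related to the procedure only | yes | yes | no, read literally | yes |
| Unlikely related | yes | no | no | yes |
| Not related | yes | no | no | yes |

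**Step 4: look for another table that names the event.** The all-AE output is broken down by arm, severity, relationship and local versus non-local, but not by system organ class or preferred term. SAEs are shown by relationship. SAP 1.0 mentions data listings in general terms but specifies none for AEs. The TEAE summary is thus the only planned one by preferred term, and the last three rows of the table have no preferred-term summary under the SAP (the last two under protocol 11.7).

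**Step 5: check that the data exist.** All AEs with onset during or after treatment are recorded (10.5.1) and coded in MedDRA (11.7, SAP 4.4). A full preferred-term table needs no new data.

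**Step 6: size.** Protocol 13.3.2 gives rates from previous trials only for AEs at least possibly related to the study injection. Neither document gives a rate for unrelated AEs or a split between product and procedure. The number of events left out cannot be derived.

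**The case against.** Several points on the other side stand.

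- The SAP is not the source of the causality rule; protocol 11.7 is. Correcting the SAP alone would leave the protocol contradicting itself.
- Because 10.5.1 restricts recording to events during and after treatment, every AE in the database is already treatment emergent by onset. The all-AE tables are in effect onset-based. Only the breakdown by preferred term is missing.
- Protocol 10.3 words its grades for the CTM and study procedure together. If the eCRF has a single causality field, CTM in the SAP may be shorthand and no procedure-only event drops out. The eCRF is not among the documents, so this part is conditional.
- Protocol section 11 describes a pilot study without formal hypothesis testing, and the TEAE table is descriptive.

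A reader might also infer that an unblinded investigator controls the filter and so biases the comparison between arms, since the Treating Physician is unblinded and most often the PI (protocol 2 and 9.2.22). The documents do not support that. Section 10.3 says Investigator, not Treating Physician. Section 9.9 gives the assessments at post-treatment visits, which include AEs, to the Blinded Evaluator. Section 15.5 counts the Blinded Evaluator among the Sub-Investigators, and section 7.2 has the Treating Physician consulted only where AE management needs it. The causal criterion, that "the AE follows a known or expected response pattern to the CTM/study procedure", covers the procedure, which saline subjects undergo as well. The one AE comparison that is tested uses all AEs without a relatedness filter.

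Nor does naming timing in the safety endpoint oblige the SAP to produce tables by onset window. The endpoint says timing is collected and promises no such table.

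**Conclusion.** The point holds as an inconsistency of definition with a limited but real consequence. Protocol 10.5.1 conflicts with protocol 11.7 and SAP 4.4, and SAP 4.4 is narrower than protocol 11.7. Followed as written, the plan never shows by preferred term the post-injection events graded unlikely or not related. Under the SAP it also never shows those attributed only to the procedure, on the assumption that the eCRF records relationship to product and procedure separately.

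No event is lost from safety reporting altogether. The omitted ones remain in the all-AE counts, in the Fisher's exact test and, if serious, in the SAE presentation. Efficacy results are untouched. The size cannot be given in numbers, because the documents contain no rates for the omitted categories. The conclusion rests on the wording alone, and the definitions should be corrected before the safety tables are programmed.

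**What to change.** Change protocol 11.7 and SAP 4.4 together:

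1. Define a TEAE as any AE with onset at or after the start of the Day 0 study procedure (arthrocentesis or injection), regardless of relationship. This agrees with 10.5.1 and makes clear that the aspiration is included.
2. Summarize all TEAEs by system organ class, preferred term and severity for each arm.
3. Present TEAEs and SAEs graded definitely, probably or possibly related to CTM and/or study procedure as a separate subset.
4. Restore the study procedure in SAP 4.4 wherever protocol 11.7 names it.

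The cost is small: wording in two documents, one changed filter and one subset table, from data already collected and coded. The protocol change goes through the amendment route in section 15.4. The downside is a longer preferred-term table that includes unrelated events; the subset keeps the related ones visible.

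### SAP 4.4 defines TEAEs, and presents TEAEs and SAEs, by relationship to the CTM alone, where protocol 11.7 uses CTM/study procedure in the same four places

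*SAP*

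**What the plan says.** SAP 4.4 ties the TEAE definition to the clinical trial material (CTM) alone: "definitely, probably, or possibly related to CTM. TEAEs will be summarized with frequencies and percentages by system organ class and preferred term". The TEAE summaries are then broken down "by system organ class and preferred term, severity, and relationship to study CTM for each treatment group". The rule for subjects with several episodes also refers to the CTM only, and for serious events "Serious Adverse Events will also be presented by relationship to the CTM". Study procedure is not mentioned anywhere in SAP 4.4.

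Protocol 11.7 contains almost the same paragraph with a wider term. Its TEAE definition reads "probably, or possibly related to CTM/study procedure", and its sentence on serious events is "Serious Adverse Events will also be presented by relationship to the CTM/study procedure". The causality rule in protocol 10.3 is equally wide: "The Relationship between an AE and the CTM and / or the study procedure will be determined by the Investigator".

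SAP 4.4 ends with a broader tabulation that has no such limit: "The number of subjects and the number of AEs will be tabulated by severity, relationship, and local injection site specific events versus non local events". Protocol 11.7 has the same sentence.

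**The concern.** The study procedure is a plausible cause of harm in this trial. Protocol 9.7 calls for an aspiration attempt in every subject, with or without visible effusion, followed by an injection into the joint. Protocol 10.5.1 has subjects questioned about complications of the procedure. Protocol 13.3.2 describes earlier related events as mostly local: injection site pain, joint swelling, joint pain. An investigator could reasonably attribute such an event to the needle or the aspiration and not to the product.

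The SAP uses relatedness to the CTM as the entry condition for being a TEAE, as well as a column in the table. A narrower causal term therefore changes which events enter the TEAE tables at all. At stake is whether the related-event and related-SAE summaries describe the intervention as it was given and agree with the protocol. (Both documents define a TEAE by causality. That is a separate question, and this mismatch exists whatever one thinks of it.)

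**Working it through.** The documents state no figure on this point, so the check is a comparison of texts.

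**Step 1. The four places, side by side.**

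| Element | Protocol 11.7 | SAP 4.4 |
|---|---|---|
| TEAE definition | CTM/study procedure | CTM |
| TEAE table axis | CTM/study procedure | CTM: "relationship to study CTM for each treatment group" |
| Multiple-episode rule | CTM/study procedure | CTM |
| SAE presentation | CTM/study procedure | CTM |

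All four differ, in the same direction. SAP 4.1 says that the SAP details the analysis in the protocol, and protocol section 11 says that it is the basis for the SAP. Neither document announces or explains a narrower causal term.

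**Step 2. If CTM and procedure are rated separately.** Take an event rated related to the procedure and not related to the CTM.

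| Output | Protocol 11.7 rule | SAP 4.4 rule |
|---|---|---|
| TEAE status | TEAE | not a TEAE |
| TEAE summaries by class and term, severity, relationship | included | absent |
| SAE presentation, if serious | related | present, shown as unrelated |
| Subjects with at least one AE, with Fisher's exact test | included | included |
| Total number of AEs | included | included |
| Severity and local/non-local tabulations | included | included |
| Final tabulation by relationship | included | included; the SAP does not say which relationship |

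**Step 3. If there is one combined rating.** Protocol 10.3 gives a single five-level scale, and each level refers to the CTM and study procedure jointly. If the eCRF follows that layout, there is no CTM-only variable. The tables in SAP 4.4 could then be filled only with the combined rating under a CTM label. No event would move, but the text would describe tables that cannot be produced as written.

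**Step 4. Can the effect be sized?** Planned arms are 99 Cingal, 99 TH and 33 placebo. Protocol 13.3.2 gives earlier rates of AEs related to the study injection:

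- Cingal 2.0%, 7.6% and 0%: 99 × 0.020 = 1.98, 99 × 0.076 = 7.52, and 0.
- TH 4.1% and 0%: 99 × 0.041 = 4.06, and 0.

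To turn these into a loss one needs the share judged related to the procedure only, and the documents do not give it. Over the whole possible range of that share, 0 to 100%, the number remaining at the 7.6% rate runs from 7.5 down to 0, which says nothing useful. The rates also refer to the study injection, so they may already leave out events attributed to aspiration only. No count follows from the documents.

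**The case against.** The strongest reply is that this is loose shorthand with little effect. Protocol 10.3 uses one scale with a joint term, so CTM in the SAP may simply be a short name for a combined rating. Local events remain visible elsewhere in SAP 4.4. The only adverse event test, Fisher's exact test on subjects with at least one AE, is not limited by relationship. Protocol 10.5.2 requires serious events to be reported to the sponsor whatever their cause. Aspiration is attempted in all arms, so there is no obvious reason for bias between arms.

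Most of this stands, and it limits the point. It does not remove it. The "and / or" wording of protocol 10.3 leaves room for separate ratings, in which case the SAP rule changes the TEAE set. With one rating, the SAP text is still wrong.

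A reader might go further in four ways that the documents do not support:

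- **That procedure-related events disappear from the safety report.** Several tabulations keep them.
- **That related counts would fall by some stated fraction, such as half.** No procedure-only share is given.
- **That separate causality ratings already exist in the data.** Protocol 10.3 promises extra detail on arthrocentesis and injection only for events already judged at least possibly related, and the eCRF is not shown.
- **That the unblinded treating physician, who is most often the PI, would blame the needle more often in the placebo arm.** That is conceivable, but nothing in the documents shows it.

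**Conclusion.** The mismatch is real, occurs in all four places, and is unexplained. It is a stated rule that conflicts with the protocol, not a missing detail. Its practical effect depends on one fact that the documents do not settle. With separate ratings, events related to the procedure only leave all TEAE summaries, and serious ones are shown as unrelated. With one combined rating, no event is reclassified but the tables cannot be produced as specified. In both cases the any-AE counts and the severity and local/non-local tabulations are unaffected. The size cannot be stated. The TEAE definition matters more than the SAE sentence, because the definition removes an event from the TEAE tables while the SAE sentence only relabels it. The correction should be made because the two documents disagree and the remedy costs almost nothing.

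**What to change.** In SAP 4.4, replace CTM with CTM/study procedure in the TEAE definition, the TEAE table axis, the multiple-episode rule and the SAE presentation, so that it matches protocol 11.7. State that the final tabulation by relationship uses the same term. If the narrower rule was intended, say so and justify it as a departure from the protocol.

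Separate columns for CTM and for procedure are an option beyond what the protocol asks for. They are possible only if the eCRF records the two ratings separately, so check the form before adding them.

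The cost is a few words in the SAP and the matching table titles. Sample size, randomization and study conduct are not affected, and the wording change itself needs no new data.
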